2.11. Secondary outcome measures

Secondary outcome variables of particular importance to aging Latino populations include the following: sedentary behavior, measured using a validated one-week recall survey responsive to change in older adults;⁵⁸ body mass index (BMI), derived using

standard clinical assessment protocols for height and weight;⁵⁰ resting blood pressure and heart rate, using standard protocols;⁵⁰ and quality of life and well-being, measured with the 10-item Vitality Plus Scale assessing well-being constructs associated with regular physical activity in aging adults, including sleep quality, energy, mood, and pain.⁵⁹

In addition to the above outcomes, program safety and adverse events are being tracked in both intervention arms using standardized forms and protocols used in prior physical activity intervention trials.^{31,36} Also, overall participant acceptability ratings of the novel Virtual Advisor intervention are being assessed at the end of the 12-month intervention period via a 19-item computer program acceptability scale,⁶⁰ a 4-item cultural congruity scale,⁶¹ and the Working Alliance Inventory's 12-item bonding subscale.^{22,62} Similar program acceptability questionnaires are being collected in the Peer Advisor arm at 12 months.³¹

2.14. Randomization of community centers to study arms

Block randomization by county locale was used to assign ten community centers to the two major study arms. Centers were randomized in pairs by locale via coin toss by staff not involved in study assessment or intervention procedures. Allocation concealment was in place for each block of centers during the randomization process to minimize selection bias with respect to subsequent blocks. Assessment staff members are blinded to randomization assignment and masked to prior assessment data for each participant.

2.15. Sample size calculation and data analysis plan

Sample size estimates have been developed to test the study's primary question related to whether the Virtual Advisor intervention is no worse than the intervention delivered by trained human advisors, i.e., a test of non-inferiority.⁶³ Using a two-tailed 95% confidence interval on the effect size (Cohen's d), the threshold of clinical significance between the two treatments, Δ , has been developed to demonstrate clinical noninferiority of the new intervention (Virtual Advisor) if the confidence interval lay completely above $-\Delta$, while clinical noninferiority of the Peer Advisor intervention will be demonstrated if the confidence interval lay completely below $+\Delta$. In this trial, the effect size (Cohen's d) is the standardized difference between the change in walking minutes/week over the 12-month intervention period. The critical value of Δ is based on a clinically meaningful difference between arms of 30 minutes of walking per week,³ and a within-arm standard deviation of 90, accounting for clustering within centers.⁶⁴ The noninferiority margin was based on a clinically meaningful difference, in one direction, between arms of 30 minutes walking/week,³ and a within-arm standard deviation of 90, accounting for clustering within centers ($\Delta=.30$).⁶⁴

We calculated that a sample of 112 per arm (224 total) would provide 80% power to demonstrate noninferiority between the two interventions using a simple pre-post analysis. We plan to use a mixed-effects linear regression model. Mixed-effects linear regression effectively addresses both missing data and early dropout in "intent-to-treat" analysis.^{65,66} In addition, the multiple assessment time points in the trial (at baseline, 6 months, and 12 months) will serve to provide more detailed information on changes over time relative to studies using pre-post assessment only.⁶⁷ Twenty-one additional participants were recruited to protect against loss to follow-up. Similar mixed-effects

linear regression techniques will be used to address the secondary outcomes of interest, e.g., intervention impacts on well-being variables across the study period.

3. Results

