2.1. Study design

The primary aim of this randomized trial is to test whether the Virtual Advisor intervention is as efficacious as the Peer Advisor intervention in promoting significant 12-month increases in weekly minutes of walking—a form of moderate-intensity activity that is readily accessible and appealing to substantial numbers of midlife and older adults across the socioeconomic spectrum.^{3,23} The study employs a cluster-randomized design of community centers located in neighborhoods with at least 20% midlife and older Latino residents.²⁴ In addition to location, other factors that were considered in choosing community centers included interest and willingness of center staff to participate in the study, appropriate space to accommodate computer equipment for the Virtual Advisor or Peer Advisor sessions, and a steady flow of Latino midlife and older adults who utilize the center's regular programs and services. Community centers were matched by geographic location and randomized to either the Peer Advisor or Virtual Advisor intervention arm. The comparative effectiveness of these two interventions constitutes the major objective of the study and is the focus of this paper. To take

advantage of the study design to begin to explore new dietary intervention strategies in this underserved population, an additional pilot substudy is also underway. As part of this pilot substudy, two other similar community centers (one in each county in which the study is located) have been selected to receive culturally adapted dietary information via mail and face-to-face modalities across the one-year study period.

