2.5. Peer Advisor recruitment and screening methods

Recruitment of Peer Advisors was accomplished using a variety of strategies. Study interventionists worked with the community center staff to identify activities within the community center through which Peer Advisors might be recruited. In addition, study staff requested referrals of people who attended the community centers regularly and who center staff identified as potentially viable candidates for the Peer Advisor role. In addition to collaborating with the community centers directly, Peer Advisor recruitment was also conducted through collaborating with different agencies external to the community centers. These agencies included local social and civic service agencies along with educational institutions such as schools and libraries. In addition, some recruitment efforts occurred through partnering with local fitness centers and targeting their physically active population as potential study peer advisors.

Peer Advisor eligibility criteria consisted of the following: (a) ages 30 years and older; (b) physically active on a regular basis (i.e., engaged in approximately 150 minutes/week or more of moderate intensity physical activity over the past 12 months); (c) free of any medical problems that might make it difficult to participate in regular physical activity or serve as a Peer Advisor in the study (e.g., any unstable chronic

conditions); (d) willing to participate in the peer advisor 12-hour training program and volunteer an average of 2-3 hours per week to advise their participants on physical activity; (e) willing to participate in monthly Peer Advisor supervision meetings; (f) able to read and understand English or Spanish sufficiently to provide informed consent and participate in all study procedures; and (g) planning to live in the area for the next 12 months. Peer Advisor selection and training consisted of screening interested individuals by phone to determine initial eligibility. Eligible individuals then attended an orientation session during which time the study objectives and procedures were explained in further detail, all questions were answered, and interested individuals provided informed consent related to study confidentiality protocols and information sharing. Individuals then completed a 12-hour Peer Advisor training program based on the successful peer-led physical activity training programs conducted previously by the Stanford team.³¹⁻³³

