2.8. Development and delivery of study interventions

The two physical activity interventions are based on the theoretically derived cognitive-behavioral advice and support strategies used in the evidence-based Active Choices physical activity counseling program and similar behaviorally based interventions in the field.³⁴⁻³⁷ The primary behavioral theory utilized in the program is Social Cognitive Theory³⁸ combined with the contextual framework of the Transtheoretical Model.³⁹ Social Cognitive Theory (SCT) recognizes the dynamic interplay of cognitive, behavioral, and social factors in influencing behavior change.³⁸ Among the variables derived from SCT are self-efficacy, the use of self-regulatory skills (e.g., self-monitoring, goal-setting), factors related to the physical activity behavior itself

(e.g., format, intensity), and social environmental factors (e.g., modeling, social support, feedback from others), as predictors of physical activity participation.⁴⁰ Applications of the Transtheoretical Model to the health promotion area include the use of a range of behavioral and cognitive strategies aimed at an individual's motivational readiness to change a particular behavior (e.g., consciousness raising and other cognitive approaches in the preparation and action phases early in the program; reinforcement management and related behavioral approaches in the later phase of the program).³⁹

The Virtual Advisor program consists of an embodied conversational agent (ECA)-- an interactive, animated computer character that simulates face-to-face counseling and support using simple speech as well as nonverbal behaviors (e.g., facial cues, hand gestures).^{41,42} (**See Figure 1.**) Individuals interact with it through touching one of several simple conversation boxes shown on the screen throughout the interaction, which eliminates the need to utilize a computer mouse, track pad, or keyboard. The conversation boxes are aimed at less than an eighth grade education level.^{41,43}

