3.3. Results related to recruitment and enrollment of Peer Advisors

During the recruitment process for Peer Advisors, 230 individuals expressed initial interest, and 119 individuals were found to be eligible based on the study's Peer Advisor eligibility criteria. Of these individuals, 56 completed the Peer Advisor training requirement, and 36 initiated Peer Advisor activities with at least one participant. Over

the course of the intervention period, six Peer Advisors had to relinquish their peer advisor activities due to a move out of the area, medical illness, or the initiation of a new job which put constraints on their time. Their study participants were transferred successfully to other Peer Advisors with minimal difficulties.

4. Discussion

The COMPASS Trial is among the first studies to systematically compare the effectiveness of physical activity advice delivered by humans versus automated advisors in aging Latino adults. Insufficiently active Latino adults are at elevated risk for a variety of chronic diseases and conditions, yet have rarely been targeted for tailored physical activity advice and support using communication sources (i.e., trained peer advisors, virtual advisors) that have great potential for population transferability and reach. The use of community centers for intervention delivery provides a readily available intervention access point in many communities across the U.S., and the one-year intervention period will provide insights related to initial physical activity adoption and more sustained behavioral maintenance. The multi-faceted recruitment plan allows for a more diverse and potentially generalizable sample, and the particularly high yield of the targeted mass mailings is notable, given its less frequent use in a number of community-based research studies. At least one study has shown that personalized direct mailings can increase response rates for Latino adults relative to non-targeted approaches.⁶⁸ While community-based *promotores de salud* (i.e., lay or peer advisors) are a known and effective mechanism for health promotion in Latino populations, the method has been limited by the ability to scale. If the technology-enabled Virtual Advisor proves comparable and cost-sensitive relative to the Peer Advisor arm, it represents a

scalable and replicable solution that could be readily integrated into current community and senior center infrastructures.

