While the primary aim of this trial is to compare the 12-month effectiveness of the Virtual Advisor relative to Peer Advisors, a similarly compelling goal is to explore, through the planned moderator analyses, which participant subgroups may do best with which type of intervention. Referred to as “the whiches conundrum”,⁶⁹⁻⁷¹ ascertaining how best to target different interventions to different subgroups of people represents among the most important challenges currently facing the behavioral health and precision medicine fields.⁶⁹ Similarly, the planned mediator analyses will provide initial information on which types of variables may be of particular importance for achieving intervention-related impacts on physical activity levels.

5. Conclusion

If the promising preliminary Virtual Advisor evidence obtained from the original pilot study²² is confirmed in this comparative effectiveness trial, this intervention will represent a potentially low-cost, readily accessible option that could be broadly disseminated across a range of community settings (e.g., clinics, pharmacies, libraries, residential settings). As such, it has substantial potential to reduce the health disparities gap by influencing a key health behavior in underserved populations.⁷²

HUMAN SUBJECTS

Note: All investigators participating in the proposed research have completed the Human Participant Protections Education for Research Teams certification process in compliance with NIH and Stanford University or Northeastern University guidelines.

I. Consent Procedures

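### Does the noninferiority rule need a within-arm condition because the aim speaks of significant increases in walking?

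*Combined protocol and SAP*

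**What the plan says.** Section 2.1 (Study design) gives the primary aim as testing whether the Virtual Advisor "is as efficacious as the Peer Advisor intervention in promoting significant 12-month increases in weekly minutes of walking". Later in the same section the comparative effectiveness of the two programs is called the major objective. Sections 1 and 4 also describe the aim as a comparison.

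Section 2.15 (Sample size calculation and data analysis plan) restates the primary question as "whether the Virtual Advisor intervention is no worse than the intervention delivered by trained human advisors" and names a noninferiority test. The measure is the standardized difference between arms in 12-month change in weekly walking minutes, with a two-tailed 95% confidence interval. The rule is "to demonstrate clinical noninferiority of the new intervention (Virtual Advisor) if the confidence interval lay completely above" minus Δ, with a mirror-image rule for the Peer Advisor. The margin is 30 minutes per week with an SD of 90 said to account for clustering; Δ is printed as .30. The analysis is a mixed-effects linear model over baseline, 6 and 12 months. Section 2.10 makes change in walking the primary outcome and adds a description of the share of each arm reaching 150 minutes per week of moderate-to-vigorous activity.

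On whether the comparator works, section 4 says peer advisors "are a known and effective mechanism for health promotion in Latino populations". Section 2.5 describes their training as "based on the successful peer-led physical activity training programs conducted previously by the Stanford team", and section 2.8 builds both programs on "theoretically derived cognitive-behavioral advice and support strategies used in the evidence-based Active Choices physical activity counseling program". No section gives an expected Peer Advisor gain in minutes per week, and none ties within-arm change to the conclusion.

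**The concern.** Read literally, the aim in section 2.1 has two parts: the programs are about equally good, and both produce significant increases. The rule in section 2.15 addresses only the first. Because it uses only a difference, it gives the same answer when both arms gain an hour a week and when neither gains anything. There is no untreated arm in the randomized comparison to tell these cases apart, and the margin rests on a clinically meaningful difference rather than on a stated share of a known Peer Advisor effect.

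At stake is the claim made from a positive result. Section 4 says: "If the technology-enabled Virtual Advisor proves comparable and cost-sensitive relative to the Peer Advisor arm, it represents a" scalable solution. Section 5 looks ahead to dissemination if the pilot evidence "is confirmed in this comparative effectiveness trial, this intervention will represent a potentially low-cost, readily accessible option". If two ineffective programs were reported as equally efficacious in raising walking, that would mislead. The apparent remedy is to make the full claim depend on a significant 12-month increase in each arm.

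**Working it through.** **Inputs.** From section 2.15: margin 30 min/week, or Δ = .30, which is .30 × 90 = 27 min; SD 90; 112 per arm; two-tailed 95% interval. From section 3.1: ten centers randomized, one lost, leaving nine. Assumption: both arms have the same true gain, tried at 0, 20, 30 and 40 min/week, because the documents give no expected gain. SD 90 is taken to cover clustering, as the plan says.

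**The plan's own figure.** n per arm = 2 × (1.645 + 0.842)² × (90/30)² ≈ 111.3, so 112. This matches, but at one-sided 0.05. The stated 95% interval corresponds to one-sided 0.025, which gives 142 per arm. That is a separate matter; the stated interval is used below.

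**Step 1: chance of declaring noninferiority at zero true difference.**
- SE of the difference = 90 × √(2/112) = 12.03.
- 30-min margin: Φ(30/12.03 − 1.96) = Φ(0.534) = 0.703.
- 27-min margin: Φ(27/12.03 − 1.96) = Φ(0.285) = 0.612.

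The common gain does not enter the formula, so these hold for any gain, including none. With no true difference, declaring noninferiority is the right answer. These figures are power, not a false-positive rate.

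**Step 2: what a within-arm condition would demand.** SE of one arm's mean change = 90/√112 = 8.50. The lower 95% limit exceeds 0 when the observed gain exceeds 1.96 × 8.50 = 16.7 min/week. With nine centers in two arms, a t quantile on 9 − 2 = 7 df (2.365) is more realistic: 2.365 × 8.50 = 20.1 min/week.

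**Step 3: chance of noninferiority and a significant rise in both arms** (simulation, 4 million draws; first figure 27-min margin, second 30-min).

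| True gain in both arms (min/week) | Noninferiority alone, normal quantile | With both-arm condition, normal quantile | With both-arm condition, t on 7 df |
|---|---|---|---|
| 0 | 61% / 70% | under 0.1% | 0.2% / 0.2% |
| 20 | 61% / 70% | 29% / 34% | 21% / 25% |
| 30 | 61% / 70% | 55% / 64% | 40% / 47% |
| 40 | 61% / 70% | 61% / 70% | 48% / 56% |

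With t on 7 df, noninferiority alone is 49% / 57%. The loss due to the condition itself is therefore about 9–10 points at a 30-min gain and 28–33 points at 20 min.

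**Step 4: what the condition would prove.** Entry requires under 100 min/week of moderate activity (section 2.2), walking is self-reported, and no arm is untreated. Some average rise from regression to the mean is therefore to be expected. If such a rise were 20 min/week in both arms with no program effect at all, the 20-min row applies: the condition would still be passed, with noninferiority, 29–34% of the time by the normal quantile. The condition screens out flat arms but does not establish that either program works.

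**Step 5: what the rule allows to be said.** Section 2.15 permits a declaration of clinical noninferiority and nothing more. No section says that this result will be reported as evidence of a significant increase. The passages in sections 4 and 5 are conditional discussion, not decision rules.

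**The case for a change.** The strongest case for a change is that this is more than the general limit of active-control trials: this protocol's own aim names significant increases, and its decision rule then drops them. Prior support for peer advising is qualitative, with no gain in minutes per week that the 30-minute margin could be shown to preserve. A flat result in both arms would be visible, but visibility is not a pre-specified rule, and a favorable headline could be written first. The remedy would cost only wording and leave the noninferiority test untouched.

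Part of this stands. The wording in sections 2.1 and 2.15 does differ, and no within-arm criterion exists anywhere in the documents. Noninferiority alone does not show that walking rose.

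The rest is weaker. The other statements of the aim, including one in section 2.1 itself, are purely comparative and agree with the rule. The phrase about increases can be read as describing what both programs are for, and the documents do not say whether significant is meant statistically or clinically. The three-time-point model yields each arm's change directly, so an analyst would report it and word the conclusion to fit. The one element that would truly alter the plan, a significance requirement in both arms, has a real cost in the chance of a positive claim and buys only an uncontrolled before-after comparison. Statisticians would reasonably disagree about that trade.

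**Conclusion.** No change to the plan follows. The difference in wording is real, but the decision rule matches the question posed in section 2.15, and the conclusion it permits is valid whether or not walking rises. The 61–70% chance of declaring noninferiority with two flat arms is the test's ordinary power at zero difference. What is left unwritten is reporting detail: the 12-month change in each arm with its 95% interval, from the planned model and allowing for clustering, set beside the main result, with the claim kept to noninferiority unless those changes support an increase. Analysts would ordinarily supply this.

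A both-arm significance condition offers no clear gain. At a true gain of 20 min/week it would roughly halve the chance of the claim (61–70% to 29–34%), and a 20-minute artefactual rise would pass it equally often. At 40 min/week it changes almost nothing by the normal quantile.

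These figures assume that SD 90 covers clustering, equal true gains in the two arms, and 112 analyzed per arm. If SD 90 leaves clustering out, the condition becomes harder to meet, which strengthens the case against adding it.

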3.1. Selection and description of study community centers

Ten community centers located in Santa Clara and San Mateo Counties, California with at least 20% Latino households (range = 21-55% Latino households) living within a one- to five-mile radius from the center were identified and expressed interest in serving as a study intervention site. These sites were block-randomized by locale to either the Peer or Virtual Advisor arms. Soon after recruitment, one center experienced unforeseen changes in its administration that disrupted center operations and precluded center participation in the study. To ensure comparable participant enrollment in each study arm, additional participants were enrolled at the remaining four community centers assigned to that intervention arm.

In each center, there were center staff who were willing to support the research team in reserving meeting space for clinical assessments, recruitment meetings, and, when relevant, Peer Advisor meetings. For the sites that received the Virtual Advisor, designated staff members were instructed on how to maintain the computer kiosk (i.e., refilling printer paper, providing minor technical support related to the computer such as making sure that it was switched on and that the touch screen remained clean, and contacting a member of the research team if needed.)

All participating community centers offered, as part of their usual activities, a nutrition program for older adults as well as nonphysical activity-oriented classes and activities, such as bingo, karaoke, and arts and crafts. Additionally, 89% offered weekly

physical activity classes and had at least one general computer available for older adults visiting their center.

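### The plan never says how baseline walking enters the primary mixed model; as a covariate it would probably narrow the noninferiority interval slightly (about 2% to 8% if the SD of 90 already includes clustering)

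*Combined protocol and SAP*

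**What the plan says.** Section 2.15 sets a noninferiority rule: "Using a two-tailed 95% confidence interval on the effect size" must clear a margin. The effect size "is the standardized difference between the change in walking minutes/week over the 12-month intervention period". The margin comes from 30 min/week and "a within-arm standard deviation of 90, accounting for clustering within centers", and is printed as .30. The section states that 112 per arm "would provide 80% power to demonstrate noninferiority between the two interventions using a simple pre-post analysis".

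On the analysis it says "We plan to use a mixed-effects linear regression model" and refers to "the multiple assessment time points in the trial (at baseline, 6 months, and 12 months"). It gives no fixed effects, random effects, covariates or covariance structure. It does not say which SD will standardize d at the analysis. Section 2.10 likewise lists baseline as one of three measurement times for the primary outcome.

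On the design, Section 2.14 states: "Block randomization by county locale was used to assign ten community centers to the two major study arms". Section 3.1 reports that one center was lost and that "additional participants were enrolled at the remaining four community centers assigned to that intervention arm".

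**The concern.** Several models fit this text: a change score, baseline as a response with arm means free, baseline as a response with a common mean, or baseline as a covariate. With complete data and an unstructured covariance, the free-means model returns exactly the change-score contrast. That contrast fixes the slope of 12-month on baseline walking at 1. When the true slope is well below 1, as is usual for self-reported activity, the change score carries avoidable noise.

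The trial's conclusion turns on whether one interval clears one margin. Interval width therefore matters, and so does fixing the model before outcomes are compared by arm. Baseline walking is already collected, so any gain costs no new data.

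**Working it through.** **1. The plan's own sample size.** n per arm = 2·SD²·(z_α + z_β)²/margin². With SD 90, margin 30 and one-sided α .05: 2·8100·(1.645 + .842)²/900 = 111.3, so 112, which matches. With the stated two-sided 95% interval: 2·8100·(1.960 + .842)²/900 = 141.3, so 142. At 112 per arm the SE is 90·√(2/112) = 12.03 and the half-width 23.6 min. Power is Φ(30/12.03 − 1.96) = 70%. These are the starting values.

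**2. Inputs the documents do not confirm.**
- 90 is the SD of change.
- The baseline SD is 91.6. This is one Table 1 row (exercise and leisure walking, all participants) standing in for the four-item outcome.
- The 12-month SD is also 91.6.
- The ICC of change is .01 to .05, and baseline explains no center variance.
- There are 245/9, about 27, participants per center.

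**3. Individual level.** With equal SDs, r = 1 − SD_change²/(2·91.6²), and the ratio of adjusted to change-score variance is v = (1 + r)/2. For SD_change 90, r = .517 and v = .759. The residual SD is 90·√.759 = 78.4.

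**4. Center level.** DE = 1 + 26·ICC. Variance ratio = [27·ICC + (1 − ICC)·v]/DE. The interval narrows by 1 − √ratio.

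*Reading A: the 90 already includes clustering, as Section 2.15 says.* The individual SD of change is 90/√DE.

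| ICC | DE | SD of change | r | v | Ratio | CI narrower | Half-width (min) | Power, 30 min |
|---|---|---|---|---|---|---|---|---|
| .01 | 1.26 | 80.2 | .617 | .808 | .849 | 7.8% | 23.6 to 21.7 | 70% to 77% |
| .02 | 1.52 | 73.0 | .682 | .841 | .898 | 5.3% | 23.6 to 22.3 | 70% to 75% |
| .05 | 2.30 | 59.3 | .790 | .895 | .957 | 2.2% | 23.6 to 23.1 | 70% to 72% |

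*Reading B: the 90 is before any design effect.* Here v = .759.

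| ICC | Ratio | CI narrower | Half-width (min) | Power, 30 min |
|---|---|---|---|---|
| .01 | .810 | 10% | 26.5 to 23.8 | 60% to 69% |
| .05 | .900 | 5% | 35.7 to 33.9 | 38% to 41% |

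These powers use 1.96. With nine centers, a t reference on 7 df (2.365) lowers them; under reading B they become 44% to 54% at ICC .01 and 24% to 26% at ICC .05.

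**5. Other 12-month SDs.** In general r = (91.6² + s² − 90²)/(2·91.6·s). Under reading B, at ICC .01 and .05, the interval narrows by 16% and 8% for s = 80, 6% and 3% for s = 100, 3% and 1.5% for s = 110, and about 0% for s = 130.

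**6. Centers that differ stably in walking level.** The change score cancels such differences; the covariate leaves a fraction 1 − .517 = .483 of them. With 5% of the level variance between centers, the variance ratio is roughly .759 + 27·.483²·(.05·91.6²)/8100 = .759 + .326 = 1.085. Other set-ups of the same case give 1.04 to 1.09. The interval would be about 2% to 4% wider (√1.04 = 1.02, √1.09 = 1.04).

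**7. The scale of the rule.** If d were standardized by the adjusted SD, power at .30 would be Φ(.30/√(2/112) − 1.96) = 61%, with or without the covariate. The margin in minutes would shrink along with the SD.

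**The case against.** The strongest reply is that the outcome is defined as change, that baseline as a repeated response is a standard analysis of change, and that every SD, correlation and ICC above is assumed. Entry was limited to people under 100 min/week of moderate activity, which makes a larger 12-month SD plausible and the gain smaller. Centers serve different neighborhoods, so stable center differences are plausible too. The covariate model also drops participants with no follow-up visit, although the plan chose a mixed model partly to handle dropout. Finally, a model with a common baseline mean would be about as efficient as the covariate model, and the text does not exclude it.

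All of this stands as a limit on the size of the gain. None of it removes the gap: the text does not choose among models that can give different intervals.

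A reader might infer three stronger things that the documents do not support.
- *That the plan commits to a change-score analysis.* It suggests one but leaves the model terms open.
- *That the covariate would lift power from 70% to 82%.* That figure, Φ(30/(78.4·√(2/112)) − 1.96), treats the 90 as containing no center variance and adds no design effect. Section 2.15 says the 90 accounts for clustering.
- *That a 5% to 10% narrowing can be relied on.* That is reading B with equal SDs, one scenario among several.

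**Conclusion.** The gap is certain; the gain is probable but small and not guaranteed. On the plan's own statement about the 90, with a 12-month SD of 91.6, ICC .01 to .05 and no stable center differences, the interval narrows by about 8% to 2%. If the 90 excludes clustering, it narrows by 10% to 5%. Over 12-month SDs of 80 to 130 the range is about 16% to 0%, and stable center differences could widen the interval by 2% to 4%. Any benefit also requires that the rule be judged in min/week or on a d with a fixed SD.

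The change is worth making because it is cheap and settles the primary model in advance. It does not rescue the trial's power. The mismatch between the 112 per arm and the stated 95% interval (142 needed), and between the printed .30 and 30/90 = .333, are separate points that matter more for power.

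**What to change.** State the primary analysis as a mixed model of 6- and 12-month walking. Fixed effects: baseline walking, arm, visit, arm-by-visit and county. Random effects: center and participant. Judge the month-12 arm difference and its two-sided 95% interval against the margin in min/week, or as d on a fixed, pre-stated SD. First reconcile 30 min with the printed .30, which is 27 min at SD 90.

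Keep the change-score contrast, with baseline as a response, as a named sensitivity analysis. It retains participants without follow-up and shows whether stable center differences matter. The two contrasts differ when baseline means differ. On the proxy row (48.0 and 43.6) the adjusted estimate would move by about −(1 − .517)·4.4 = −2.1 min, which is minor here.

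The cost is one paragraph in the analysis plan, fixed before outcomes are compared by arm, plus a decision on the scale of the rule. It needs no new data or visits. The price is the loss of participants with no follow-up visit from the primary model and the chance that precision does not improve.
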